2.1. Study Rationale

The current treatments for TB have a lengthy duration, involve multi-drug regimens, must be taken multiple times per day and have non-trivial unwanted effects.^{4,5} Furthermore, some of the available drugs are expensive. Two of the main consequences of this profile are - first, TB treatments require large commitments of resources and infrastructure, typically lacking in the countries where TB is most prevalent, and second, poor compliance is common, which results in increased severity of disease and mortality and in the emergence of drug-resistant strains.⁴⁻⁶

The shortcomings of the available treatments, combined with massive prevalence, health impact and mortality of TB (see below), make a strong case for the discovery and development of novel TB drugs and drug regimens that will address the challenges of current treatments through one or more of the following features: shorter treatment duration, reduced dosing frequency, improved safety and tolerability profile, improved efficacy, greater affordability, suitability for pediatric use and for co-administration with antiretroviral therapy in individuals co-infected with Mtb and HIV.

Encouraging preclinical data and a sustainable safety and tolerability profile (see Section 2.3) of the first trial in healthy volunteers (TBA7371-001) justify the evaluation of TBA-7371 in an EBA trial in adult patients with untreated, drug-sensitive pulmonary TB.

2.2. Background

2.2.1. Tuberculosis

Tuberculosis in humans is an infectious disease caused by *Mtb*, which typically affects the lungs (pulmonary TB) but can affect other sites as well (extrapulmonary TB). It is an airborne disease transmitted by inhalation of infective droplets containing *Mtb* and expelled into the air by a person with active TB via coughing, sneezing, or even talking. The unique cell wall of *Mtb*, which has a waxy coating primarily composed of mycolic acids, allows the bacillus to lie dormant in some individuals for many years (i.e., latent TB infection). Latent TB infection (LTBI) is not associated with symptoms and is not infectious. However, approximately 10% of individuals with LTBI will develop active disease during their lifetime (i.e., a 10% lifetime risk of activation), often years or even decades after the initial infection and most of these cases will themselves become infectious.⁷ Individuals with LTBI who are co-infected with HIV are at an increased risk of developing active TB; such individuals are estimated to have an 8% annual risk of reactivating LTBI.^{8,9} Tuberculosis is currently one of the top three killer infectious diseases, and there is more TB in the world today than at any other time in history. While TB is found in every country in the world, it disproportionately affects people in resource poor settings, particularly those in Asia and Africa. Nevertheless, TB outbreaks still occur in industrialized nations. The World Health Organization (WHO) estimates that 2 billion people, approximately one-third of the world's population, are infected with *Mtb* worldwide. In 2015, there were an estimated 10.4 million new incident cases of TB (11% co-infected with HIV), and 1.4 million people died from TB.¹⁰

2.2.2. Early Bactericidal Activity Clinical Studies

The ability of EBA studies to quantify the bactericidal action of anti-TB agents alone or in combination was established following a pioneering study in 1980.¹¹ In these studies, which typically have treatment periods ranging from 2 to 14 days, the ability of various agents and combinations of agents to decrease the number of CFU of *Mtb* present in the sputum of study participants serves as an indication of the anti-TB activity of the treatment. A review of EBA studies conducted on the key anti-TB drugs has shown the value these studies offer to demonstrate the early anti-TB effect that a new therapeutic agent may have and to explore the relationships between dose, pharmacokinetics and bactericidal activity in patients.¹²

2.3. Benefit/Risk Assessment

In this trial patients with untreated, drug-sensitive pulmonary TB will receive for 14 days either the test drug TBA-7371 in 1 of 5 regimens (from 100 mg QD to 400 mg QD) or commercial HRZE fixed combination (Rifafour® e-275) as control drug, dosed as recommended in the package insert.¹

HRZE is a first line treatment for drug sensitive TB with a well-established, generally favorable, yet not straightforward, benefit-risk profile. The most common AEs associated with HRZE are peripheral neuropathy, optic neuritis, hepatitis, and gastro-intestinal AEs (see Package Insert¹ and 2018 Safety Update² enclosed in study specific manual(s)).

TBA-7371 was tested in adult healthy volunteers in 1 clinical trial (TBA7371-001), composed of three parts: a single ascending dose (SAD) part where single doses from 100 to 800 mg were

tested, a multiple ascending dose (MAD) part where 100, 200 and 400 mg QD were taken for 14 days and a drug-drug interaction (DDI) part. The most common treatment-emergent adverse events (TEAEs) were increase in heart rate associated with decrease in blood pressure and eye symptoms (blurred vision, photophobia, altered color vision, increased lacrimation). The frequency of such events was dose related, starting at doses above 100 mg /day. Most were mild and transient. In particular, vision-related AEs were of short duration, resolved before the next dose and were not persistent changes. Furthermore, tachyphylaxis to changes in heart rate and blood pressure appeared to occur in the MAD part of the trial.

The eye symptoms appeared to be associated with C_{max} . It is therefore possible that the tolerability profile could improve with fractionation of the daily dose. This justifies the inclusion of the BID and TID dosing regimens in this trial.

There is no information on the efficacy of TBA-7371 in humans. PK/PD modelling from animal experiments, supplemented with additional PK data from healthy human subjects, suggests that bactericidal effect could be present at 100 mg/day and then increase with dose.

More information on TBA-7371 is provided in the Investigator Brochure.

The overall risks associated with TBA-7371 at or below 400 mg QD are considered low and are mitigated by the following design features of the present protocol:

- throughout the 14-day Treatment Phase eye symptoms, visual acuity and color vision, ECG will be assessed/recorded every 3-4 days, vital signs daily;
- the escalation from QD dose level to the next will be staggered, and escalation decisions will be taken by an IDMC based on full unmasked safety data from the lower dose cohort(s);
- it is possible that patients will experience no meaningful bactericidal effect for the duration of treatment with TBA-7371 of 14 days. Participants will thus be kept under close observation in hospital for the entire period so that in case of progression of disease, effective treatment can be initiated without delay;
- at the end of Study Treatment Phase patients will be switched to standard of care TB treatment, trained on the importance of compliance and proper follow-up and followed for an additional 28 days (Follow-up Phase of the study).

Given the safety profile observed thus far and the design features described above, the benefit-risk assessment for this trial is considered favorable.

3. Objectives and Endpoints

3.1. Primary Objectives and Endpoints

Table 5. Primary Objectives and Endpoints

Objectives	Endpoints
Bactericidal activity	
Demonstrate the 14-day EBA from screening (“0”) to Day 14 (EBA 0-14) of 5 dose regimens of TBA-7371 monotherapy and HRZE as assessed by CFU counts on solid media culture.	
 Slope, i.e. average change per day, from screening (“0”) to Day 14 [BA_{CFU}(0-14)] of the log CFU counts.
Safety	
Assess the severe/SAE burden of 5 dose regimens of TBA-7371 monotherapy and HRZE over a 14-day treatment period.	
 Frequency of study participants who experienced one or more severe AEs (\geq grade 3) and/or SAEs from Day 1 through Day 15.

3.2. Secondary Objectives and Endpoints

Table 6. Secondary Objectives and Endpoints

Objectives	Endpoints
Bactericidal activity	
Demonstrate the EBA of the first 2 days (screening [“0”] to Day 2) and of the remaining 12 days (Day 2 to Day 14) of 5 dose regimens of TBA-7371 monotherapy and HRZE, as assessed by CFU counts on solid media culture.	
 Slope, i.e. average change per day, from screening (“0”) to Day 2 [0-2] and from Day 2 to Day 14 [BA_{CFU}(2-14)] of the log CFU counts.
Demonstrate the bactericidal activity of 5 dose regimens of TBA-7371 monotherapy and of HRZE, as assessed by alternative methods: 
 time to sputum culture positivity (TTP) in (MGIT) culture LAM assay 	
 Slope of the time to sputum culture positivity (TTP) in the MGIT system from screening (“0”) to Day 14 [BA_{TTP}(0-14)], from screening to Day 2 [BA_{TTP}(0-2)], and from Day 2 to Day 14 [BA_{TTP}(2-14)]. Slope of the log concentration of sputum LAM from screening (“0”) to Day 14 [BA_{LAM}(0-14)], from screening to Day 2 [BA_{LAM}(0-2)], and from Day 2 to Day 14 [BA_{LAM}(2-14)].
Safety	
Assess the adverse event (AE) profile of each dose regimen of TBA-7371 and HRZE over the 14-day treatment period.	
 Frequency from Day 1 through Day 15 of participants with AE and frequency of AEs: overall, by body system, and preferred term; by seriousness, intensity (severity), expectedness and relatedness to study drug.
Assess the impact on eye symptoms, visual acuity and color vision of each dose regimen of TBA-7371 and HRZE over the 14-day treatment period.	
From Day 1 through Day 15:
 
 Frequency of participants with any new (vs. screening) eye symptom in one or both eyes. Mean and frequency distribution of duration of each eye symptom.

Objectives	Endpoints
	
 Mean and frequency distribution of percentage of days with any eye symptom and each of the eye symptoms. Mean/median change in visual acuity score from screening to lowest score during Days 1-15. Frequency of participants with any new color vision abnormalities (tritan, protan, deutan) in one or both eyes and degree of severity (mild, moderate, severe).
Assess the impact on heart rate, blood pressure and ECG profile of each dose regimen of TBA-7371 and of HRZE over the 14-day treatment period.	
From Day 1 through Day 15:
 
 Mean and frequency distribution of changes in HR, SBP and DBP as measured by the following 2 (BP) or 3 (HR) methods: 
 manual (vital signs), after at least 10 minutes in supine position (“manual, supine”); manual, after 2 (± 0.5) minutes in standing position (“manual, 2-min standing”); HR from ECG, supine position (“ECG, supine”) Frequency of participants with $\ge 25\%$ increase in HR, decrease in SBP, decrease in DBP vs. baseline as measured with any of the methods described above. Mean and frequency distribution of percentage of days with $\ge 25\%$ increase in HR, decrease in SBP, decrease in DBP vs. baseline. Mean/median change from screening through Day 15 in PR, RR, QRS, QT, QTcF values from baseline ECG.
Assess whether there is tachyphylaxis over the 14-day treatment period for HR, SBP, DBP and eye symptoms.	
 Mean change in HR, SBP and DBP from Day 1 to Days 4, 7, 10, 14 and 15 for each of the measurement methods described above. Change in frequency of participants with eye symptoms (all, severe, serious) and change in mean visual acuity score and frequency of color vision changes from Day 1 to Days 4, 7, 10, 14 and 15.
Assess whether cardiovascular and/or ophthalmic adverse events persist or recur up to 4 weeks after discontinuation of treatment with TBA-7371.	
 Mean change in HR, SBP and DBP from screening to Days 28 and 42 and from Day 14 to Days 28 and 42 for each of the measurement methods described above. Change in frequency of participants with eye symptoms (all, severe, serious) and change in mean visual acuity score and frequency of

Objectives	Endpoints
	color vision changes from screening to Days 28 and 42 and from Days 1-15 (combined) to Days 28-42 (combined).
Assess whether there are meaningful changes in safety laboratory measurement	For each blood/serum and urine parameter: 
 • Mean, median, highest and lowest value. • Shift tables from screening to Day 3, Day 7, Day 14 and Day 42.
Secondary, PK and PK/PD	
Evaluate the pharmacokinetics of TBA-7371 monotherapy over the 14-day treatment period.	
 • TBA7371 concentration profiles and PK parameters over the 14-day treatment interval: C_{max}, T_{max}, C_{last}, T_{last}, AUC_{inf}, AUC_{last}, AUC_{tau}, C_{min}, half-life, accumulation ratios.
Identify the lowest exposure to of TBA-7371 associated with maximal EBA effect.	
 • Expected concentration associated with 90% of the maximal TBA-7371 EBA effect (EC90)

3.3. Exploratory Objectives

Details of exploratory objectives will be included in separate operational and/or analysis plans. Results of exploratory objectives may be reported separately from the main clinical study report.

Exploratory objectives may include but are not limited to:

- exploration of the correlation between EBA and biomarkers such as mycobacterial cell-free DNA, ribosomal RNA ratio assay, sputum and/or peripheral blood gene expression profiles and serum cytokines or other proteins, urine LAM, and bacterial genotypic evaluations for emergence of resistance;
- testing of susceptibility to TBA-7371 (MIC);
- population PK modeling.

4. Study Design

4.1. Overall Study Design

This is an interventional, 5-cohort, 3-step dose escalation clinical trial in adult patients between 18 to 60 years of age with rifampicin-sensitive pulmonary TB.

The escalation will occur sequentially in 3 steps: from Cohort I to Cohorts II and III, from Cohorts II and III to Cohort IV and from Cohort IV to Cohort V (see below). Within the 2nd escalation step, participants will be randomized equally (1:1) to Cohort II or Cohort III, which have the same total daily dose (200 mg, see below). Within each cohort, participants will be randomized unequally (5:1) to TBA-7371 or HRZE (isoniazid [H] / rifampicin [R] / pyrazinamide [Z] / ethambutol [E]) fixed dose combination tablets. Rifafour® e-275 (Sanofi) tablets, a commercial presentation of HRZE approved and available in South Africa, will be used in this study.^{1,2}

Each participant will undergo 3 study phases: up to a 7-day Screening Phase with no TB treatment, a 14-day Study Treatment Phase on TBA-7371 or HRZE and a 28-day Follow-up Phase on standard of care TB treatment.

The doses and dose schedules of the 5 TBA-7371 cohorts will be as follows: Cohort I: 100 mg QD, Cohort II: 100 mg BID, Cohort III: 200 mg QD, Cohort IV: 100 mg TID, Cohort V: 400 mg QD. For HRZE, the dose will be weight-based as per package insert.¹

An IDMC will make dose escalation recommendations. After the last Cohort I participant completing the Study Treatment Phase (Day 14), the IDMC will decide whether Cohort II and Cohort III can start enrolment (1st escalation step). The same approach will be taken for the 2nd escalation step (from Cohorts II & III to Cohort IV) and for the 3rd escalation step (from Cohort IV to Cohort V). For each escalation step, the “go / no-go” decision will be based on accumulating safety data. Additional data (e.g. PK) may be provided as supporting evidence.

Authorized study site personnel will dispense each dose of study drug.

This study will be open label for study participants, study site personnel, IDMC members, laboratory personnel involved in PK measurements and all sponsor and CRO personnel.

The study will instead be masked (blinded) for personnel involved in the conduct of all other laboratory procedures (including those for the primary endpoint).

Study participants will be hospitalized during the Screening Phase and will remain in hospital until the day after the last dose of study drug is dispensed (Day 15). Written informed consent must be given before any screening procedure is started. Participants will leave the hospital on Day 15 after all procedures scheduled for that day have been completed. Thereafter, participants will undergo scheduled visits on Days 28 and 42 (+/- 3 days) as outpatients during the Follow-up Phase.

Candidates will be screened to achieve 90 randomized study participants. Within each dose escalation cohort, 18 participants will be randomly assigned in a 5:1 ratio to TBA-7371 (N=15) or HRZE (N=3). The total sample size of the HRZE group (all cohorts combined) will be 15, assuming all cohorts will be allowed to undergo treatment.

Within each cohort, there will be no replacement for the first 2 early withdrawals (drop-outs) occurring during the Treatment Phase. Drop-outs from the 3rd onwards will be replaced to ensure that the total number of participants completing study treatment in each cohort is at least 16. Participants who withdraw prematurely during the Follow-up Phase will not be replaced.

4.2. Scientific Rationale for Study Design

The dose escalation approach, with go/no-go decision on each escalation step to be taken by the IDMC based on the complete safety dataset from lower dose cohort(s), has been chosen to maximize the safety of participants, against the background of the safety and tolerability profile observed in study TBA-7371-001. As mentioned above, the two most frequent treatment emergent adverse events, namely heart rate increase and eye symptoms, had a dose-dependent (above 100 mg QD) frequency and were mostly mild and transient.

The level of masking, in this study, which includes all personnel involved in CFU counts for the primary endpoint (see Section 6.3.2), ensures balance of methodological excellence and feasibility, and is considered adequate for the stage of development of TBA-7371.

Whereas the 3 dose escalation steps will be conducted in an open-label manner, within the 2nd escalation, participants will be randomized to Cohort II or Cohort III. This approach is justified because Cohorts II and III have the same total daily dose of TBA-7371 (200 mg) and strengthens the design of the study.

Within each cohort, participants will be randomized to TBA-7371 or HRZE control with a 5:1 ratio (15 TBA-7371 vs. 3 HRZE). This unequal randomization is justified by the fact that HRZE data from all cohorts will be pooled; hence, if all 5 cohorts will be allowed to enter the trial, the target size of the control group (N=15) will be the same as the TBA-7371 groups.

The target population is adult males and females with untreated, rifampicin-sensitive, uncomplicated pulmonary TB. This population is ideal for the assessment of the bactericidal activity of a new drug.

In this trial, QD, BID and TID schedules will be tested. The scientific rationale is that some symptoms appear to be associated with C_{max}. It is therefore possible that fractionation of the daily dose could improve the tolerability profile and the benefit-risk ratio.

Primary endpoints are: 1) EBA of TBA-7371 as determined by the slope of log CFU count on solid media culture from screening through Day 14; and 2) frequency of participants with serious and/or severe (\geq Grade 3) AEs throughout the treatment. The value of EBA to predict clinical efficacy is outlined in Section 2.2.2. Combined SAEs and severe AEs are considered the best indicators of the overall burden and acceptability of the treatment to patients.

The scientific rationale for secondary endpoints is as follows:

- EBA as assessed by alternative methods [TTP in MGIT culture and LAM assay]. MGIT culture and LAM assay are easier to conduct compared to solid media culture. Hence, insight into the suitability of such methods to replace solid media culture will be useful for this and other TB drug development programs.
- Full AE assessment. All AE will be assessed by seriousness, intensity (severity), relationship to study drug and expectedness based on the information provided in the

Investigator Brochure and summarized by body system and preferred medical term. This will allow the full safety and tolerability profiling of TBA-7371.

- Assessment of heart rate and blood pressure via vital signs and ECG, eye symptoms, visual acuity and color vision. These measurements were selected based on the safety profile that emerged from animal studies and from phase 1 study TBA7371-001 (see above). Multiple assessment methods will be carried out for cardiovascular variables to maximize the sensitivity of the study. Eye symptoms will be assessed by non-leading questions delivered by trained staff based on a standardized script. Visual acuity and color vision will be assessed through standardized procedures. The possibility of decrease (tachyphylaxis) or increase over time of these unwanted effects, as well as their persistence or recurrence in the month following discontinuation of study drug, will also be assessed: results of study TBA7371-001 suggest changes over time during treatment with TBA-7371 of cardiovascular (decrease) and eye (increase) adverse events. It should be noted that all eye symptoms reported study TBA7371-001 were transient.

PK profile and relationship between exposure and magnitude of EBA. So far, the PK profile of TBA-7371 has been only studied in animals and in healthy volunteers. This study allows the confirmation of the PK profile in TB patients. The relationship between exposure and bactericidal response will guide the selection of the dose regimen(s) for further development of TBA-7371. No active metabolite of TBA-7371 has been identified so far, and no major metabolite seen in humans has been detected at more than 10% of parent TBA-7371. Therefore, TBA-7371 metabolism will not be examined further in this study.

Additional measurements may be added as exploratory endpoints. Exploratory endpoints will be the object of separate documents.

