8.2. Bactericidal Activity Assessment

8.2.1. Overnight Sputum for EBA assessment and Exploratory Measurements

Overnight sputum will be collected from 3 PM to 7 AM of the following morning.

The overnight sputum samples collected on Day -2 and Day -1 of the Screening Phase will be used to determine baseline EBA. Subsequent overnight sputum samples will be collected every day/night (Day 1 to Day 14) to assess changes in bacterial burden during the Study Treatment Phase.

Early bactericidal activity will be assessed on each sputum sample by 3 different methods: 1) CFU on solid media culture (primary), 2) time to sputum culture positivity (TTP) in MGIT culture, 3) LAM assay. Confirmation of Mtb will be performed on solid media and MGIT cultures as necessary using available commercial methods.

A commercial molecular test to assess isoniazid and rifampicin sensitivity, GenoType MTBDRplus (HAIN Lifesciences), will be utilized on positive MTB cultures from Day -2 (or, if Day -2 unavailable, Day -1) and Day 14 to assess the drug susceptibilities at each visit. In addition, MICs of TBA-7371 will be batch tested on positive MTB cultures from Day -2 (or, if Day -2 unavailable, Day -1) and Day 14.

Extra samples from overnight sputum collections, as well as MTB isolates from cultures, will be stored for potential assessment of exploratory endpoints (see Section 8.10).

Details on sputum collection, handling and testing procedures, and on the laboratory are provided in the laboratory study instruction document.

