9.4.1.2. Secondary Bactericidal Activity Analyses

EBA measures (BA_{CFU}(0-2) and BA_{CFU}(2-14)) will be calculated from the regression models and assessed similarly as described above for BA_{CFU}(0-14). MGIT TPP and concentrations of LAM will also be assessed similarly. For all secondary EBA measurements there will be no adjustment for multiple comparisons and no formal success criteria.

All efficacy analyses will be performed in the mITT population, with sensitivity analyses performed in the per-protocol population to assess the robustness of results.

One of the limitations of the primary analysis method is that each individual subject must have enough data to fit a bilinear regression model in order to be included in the primary analysis. More sophisticated statistical models, such as a Bayesian nonlinear mixed-effects regression model ¹³ do not have this same limitation, and will therefore be examined through sensitivity analyses to assess the robustness of the primary model fits. The Bayesian model jointly fits the data from all patients and treatment groups and comprises the joint bilinear regression model as a special case. In addition, similar bilinear and linear regressions will also be fit directly to the change from screening response variable to further assess the robustness of the results.

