11.2 Secondary Efficacy Endpoints

11.2.1 Time to Sputum Culture Positivity

When time to sputum culture positivity for a participant is not concluded by Day 42 (i.e., > 42 days), the value will be defined to be 43 days. For each participant, linear and bilinear regression models will be fit, and the better fit model based on lower AIC similarly as described for BACFU(0-14) in [Section 11.1.1](#) will be used to estimate BATTP(0-14), BATTP(0-2) and BATTP(2-14) of TTP from Screening to Day 14, Screening to Day 2 and Day 2 to Day 14, respectively. BATTP(0-14), BATTP(0-2) and BATTP(2-14) will be analyzed using an ANCOVA model, with a fixed effect for treatment group and baseline TTP as a covariate. An ANCOVA model will be used to quantify the evidence that each of the treatment group mean BATTP(0-14), BATTP(0-2) and BATTP(2-14) is less than 0.

Mean and mean change from baseline of TTP with 95% CI at each time point will be presented in line plots by treatment group. In addition, observed and fitted lines of bilinear and linear regression models of TTP over time will be presented for each participant.

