11.2.2 Sputum Lipoarabinomannan

When a value of concentration of sputum LAM is < lower limit of quantification (LLOQ), the value will be defined to be half of LLOQ. For each participant, linear and bilinear regression models will be fit, and the better fit model based on lower AIC similarly as described for BACFU(0-14) in [Section 11.1.1](#) will be used to estimate BALAM(0-14), BALAM(0-2) and BALAM(2-14) of log concentration of sputum LAM from Screening to Day 14, Screening to Day 2 and Day 2 to Day 14, respectively. BALAM(0-14), BALAM(0-2) and BALAM(2-14) will be analyzed using an ANCOVA model, with a fixed effect for treatment group and baseline log value of concentration of sputum LAM as a covariate. An ANCOVA model will be used to quantify the evidence that each of treatment group mean BALAM(0-14), BALAM(0-2) and BALAM(2-14) is less than 0.

Geometric mean and geometric mean ratio of post-baseline to baseline of concentration of sputum LAM with 95% CI at each time point will be presented in line plots by treatment group. In addition, observed and fitted lines of bilinear and linear regression models of log concentration of sputum LAM over time will be presented for each participant.

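### TTP and sputum LAM are justified by the insight they give into replacing solid-culture CFU, but no analysis in the protocol or SAP relates either one to CFU

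*Protocol*

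**What the plan says.** Protocol section 4.2 gives a reason for each group of secondary endpoints. For TTP in MGIT culture and the LAM assay, it says that both are easier to run than solid culture and that "insight into the suitability of such methods to replace solid media culture will be useful" for this and other programmes. It gives no other reason for them.

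Protocol section 8.2.1 makes the data paired by design: "Early bactericidal activity will be assessed on each sputum sample by 3 different methods". The EBA samples are the two screening collections (Days -2 and -1) and the 14 daily collections on treatment.

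The formal objective in protocol section 3.2 is worded differently from the rationale: "Demonstrate the bactericidal activity of 5 dose regimens of TBA-7371 monotherapy and of HRZE, as assessed by alternative methods". Its endpoints are the TTP and LAM slopes.

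For the analysis, protocol section 9.4.1.2 says "MGIT TPP and concentrations of LAM will also be assessed similarly", with no multiplicity adjustment and no success criterion. SAP 11.2.1 fits an ANCOVA to the TTP slopes "with a fixed effect for treatment group and baseline TTP as a covariate". SAP 11.2.2 does the same for LAM "with a fixed effect for treatment group and baseline log value of concentration of sputum LAM as a covariate". Protocol Table 9 and both SAP sections state the question as whether each group mean is below zero.

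**The concern.** A mean slope that differs from zero shows that a method detects change under treatment. It does not show that the method follows CFU from one participant to the next, orders the regimens as CFU does, or is comparably precise. Suitability as a replacement depends on those properties. A method could differ clearly from zero in every group and still rank participants or regimens differently from CFU.

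The plan collects paired data, derives the slopes, and then specifies no estimate that sets one method against another. If someone later wants to comment on replacement, the measure of agreement would have to be chosen after the data are seen.

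**Working it through.** The documents give no figure for between-method agreement, so there is none to reproduce. The check has two parts.

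**1. Is any between-method analysis specified?** These are the places where one could appear:

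- Protocol 9.4.1.2 and Table 9: one slope per participant, then ANCOVA of each group mean against zero, separately for CFU, TTP and LAM.
- SAP 11.2.1 and 11.2.2: the covariate is the method's own baseline. CFU enters neither model. The line plots and fitted curves are drawn for each method separately.
- SAP 11.1.3 and 11.5 (sensitivity) and 11.3 (subgroups): none compares methods.
- Protocol Table 9, protocol 9.5 and SAP 13.2: CFU is correlated with PK exposure only (AUC, Cmax, time above MIC).
- Protocol 3.3 and SAP 5.3 (exploratory): "exploration of the correlation between EBA and biomarkers such as mycobacterial cell-free DNA, ribosomal RNA ratio assay", followed by gene expression, serum proteins and urine LAM. MGIT TTP and sputum LAM are not named. SAP 9.2 counts both among the EBA measurements, so in that item they fall on the EBA side of the correlation.

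Number of analyses in the protocol or SAP that relate TTP or sputum LAM to CFU: 0.

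**2. What could the paired data show?** Inputs: 90 randomised participants (75 on TBA-7371, 15 on HRZE) in six treatment groups, and 16 EBA samples each. Full collection gives 90 × 16 = 1,440 samples read by all three methods, and up to 90 slope pairs for each comparison with CFU.

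The approximate 95% CI for a correlation r adjusted for k group indicators is tanh(atanh(r) ± 1.96/√(n − 3 − k)). The values of r are assumptions, since the documents give none.

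- n = 90, k = 5: 1.96/√82 = 0.216.
  - r = 0.7: tanh(0.867 ± 0.216) = 0.57 to 0.79.
  - r = 0.5: tanh(0.549 ± 0.216) = 0.32 to 0.64.
- n = 80 (the replacement rule secures at least 16 completers in each of five cohorts, 5 × 16), k = 5: 1.96/√72 = 0.231.
  - r = 0.7: 0.56 to 0.80.
  - r = 0.5: 0.31 to 0.65.
- One regimen, n = 15, k = 0: 1.96/√12 = 0.566.
  - r = 0.7: 0.29 to 0.89.
  - r = 0.5: -0.02 to 0.81.

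A pooled within-group estimate would be informative and a single-arm estimate would not. That is a reason to name the pooled form in advance.

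**Direction of the slopes.** CFU and LAM fall when a regimen is active. TTP lengthens, so its slope is positive. Protocol Table 9 and SAP 11.2.1 nevertheless ask whether the mean TTP slope is below zero. Read literally, an active regimen would appear to succeed on CFU and fail on TTP, which weakens even a comparison by eye.

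**The case against.** The strongest reply is that replacement is mentioned in one sentence of rationale and is not a listed objective or endpoint. This is correct. The listed objective is to show activity by alternative methods, and that has an analysis. A reader might infer that the trial cannot support the purpose for which these endpoints were included, or that the replacement question must go unanswered. The documents do not support either inference: they promise insight, not a conclusion about replacement.

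Secondly, the exploratory list is expressly open-ended, and its details are left to separate plans that are not among the documents. A reader might take the omission of TTP and sputum LAM from that list as proof that no comparison is planned. It is not proof, and the statement has to stop at the protocol and SAP. Still, protocol section 9.4 places secondary endpoints in the SAP and exploratory ones elsewhere. TTP and sputum LAM are secondary, so the SAP is where a reader would look.

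Thirdly, the outputs go beyond tests against zero. The ANCOVA code in SAP Appendix 4 gives group means with 90% CIs, written for the CFU slope but carried over to the other methods. Time-course plots and individual fitted curves are planned for each method, and derived parameters will be listed. A reader can set these side by side. That stands, but it remains an informal reading of six means per method with no stated measure of agreement.

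Finally, a correlation does not settle the matter. Participant slopes are estimated with error, which pulls correlations towards zero, and a high correlation would not by itself show that a method can replace CFU. This also stands and is built into the change proposed.

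**Conclusion.** The point holds within limits. The protocol's only stated reason for the TTP and sputum-LAM endpoints has no matching analysis in the protocol or SAP, although the three methods are paired on each sample and the slopes are already derived. What is available is an informal look, and the stated direction of the TTP test makes that harder.

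The consequence is modest. The primary analysis, safety and dose escalation are unaffected, and the formal secondary objective is met. What is forgone is a between-method estimate with a 95% CI of about 0.57 to 0.79 at r = 0.7, or 0.32 to 0.64 at r = 0.5. These figures assume the r values, 90 evaluable participants, all five cohorts opened, and a common within-group correlation. They widen if fewer are evaluable, for example through contaminated cultures or a cohort that does not open. This change should be made, but nothing else depends on it.

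**What to change.** Add a short subsection to SAP 11.2, in the mITT population, labelled descriptive and without a success criterion.

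First, define one sign convention for all slopes, for example by reversing TTP so that a negative slope means activity for every method, and reconcile the direction of the TTP test in SAP 11.2.1 and protocol Table 9 with it. Then specify:

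1. The treatment-adjusted (within-group) Pearson and Spearman correlations of participant BA_TTP(0-14) and BA_LAM(0-14) with BA_CFU(0-14), with 95% CIs. Adjustment matters because an unadjusted correlation would mix differences between regimens with association between participants.
2. A plot and rank comparison of the group mean slopes by method.
3. Standardised activity (group mean slope divided by its SD) by method.

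State that these analyses address the rationale in protocol section 4.2, that error in the estimated slopes attenuates the correlations, and that a high correlation alone does not establish replacement. If a separate exploratory plan already contains this comparison, a cross-reference in SAP 11.2 is enough.

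Cost: SAP wording and a few extra tables and figures. No new samples are needed and the primary analysis does not change.
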